3. STUDY DESIGN

The purpose of the proposed study is to determine whether yoga is an effective method for treating GAD, and its relative efficacy compared to a standard psychosocial intervention. For this purpose, we will conduct a randomized controlled trial. Using superiority tests, yoga (N = 95) will be compared to SE (N = 40), a commonly used control condition. Using non-inferiority tests, yoga will compared to standard CBT for GAD (N = 95). To improve comparisons, all interventions will be conducted in a group format over 12 weekly sessions with 4-6 patients per group and therapists/yoga instructors. We anticipate having approximately 3 yoga instructors, 3 CBT therapists, and 3 SE instructors, along with 2 IEs per enrolling site. All interventions will be conducted at anxiety out-patient clinics in Boston (the Center for Anxiety and Related Disorders at Boston University and the Center for Anxiety and Traumatic Stress Disorders at Massachusetts General Hospital). The third study site, NYU Langone Medical Center in New York City, will not recruit participants and will conduct data analysis and interpretation as well as study oversight. Subjects in all 3 treatment groups will be provided with a credible rationale for the efficacy of their assigned treatment. At each study treatment visit, patients will complete various psychological measures. Some of the study visits require more in-depth assessments involving saliva sample collection, meeting with a study doctor, and a physical examination (see the section 6.1 for more information). The four independent evaluator blinded assessments occur pre-treatment (baseline visit), mid-treatment (Week 6), post-treatment (Week 12), and at a sixmonth follow-up.

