7.1 Specification of Safety Parameters

A study MD or nurse with MD oversight will assess medical history and with consent will consult with PCPs if any medical issues that may potentially interfere with safe participation in yoga are identified. We have modified our study criteria to more clearly exclude all potential subjects with physical disabilities (evaluated with a medical history and physical exam) or cognitive disabilities (evaluated by the Montreal Cognitive Assessment Scale) that would clearly preclude safe practice of the yoga intervention or CBT. At present there is insufficient information regarding the safety of yoga during pregnancy. For reasons of safety, all women of childbearing potential will be required to use a reliable form of birth control throughout the study: (e.g.: oral contraceptives, surgical sterilization (of the subject or of her male partner), IUD (intrauterine device), condom and spermicide or diaphragm and spermicide). Subjects with existing or planned pregnancy during the intervention will be excluded. Inclusion of subjects

with any minor preexisting conditions of potential concern will be subject to participation only after consented review with and approval by the subject's primary healthcare provider.

Each visit, adverse events will be assessed on the adverse events monitoring form and rated as mild, moderate, or severe (as defined in AE section below). On weeks 0, 2, 4, 8, 10 and 12 the CGI-S, CGI-I, BDI and a suicidality checklist will be administered to evaluate any potential worsening symptoms. Physical fitness will be assessed by the study nurse with MD oversight or MD with the medical history form and a standard physical exam, emphasizing musculoskeletal, neurologic and cardiac history.

Twenty-four-hour emergency coverage with a study clinician (physician, psychologist or registered nurse with MD oversight) will be available. Patients will be provided with cards with the emergency contact number. In the event of an emergency the clinician will determine the necessary clinical intervention and will provide and coordinate appropriate care.

Parameters

All three interventions (Yoga, CBT, and SE) are safe interventions with minimal associated risk.

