9.2 Sample Size and Randomization

A non-inferiority test is the most direct test of our hypothesis that Yoga will be as effective as CBT for both short-term and long-term outcomes. We will perform a non-inferiority test using response rate (response rate is defined as CGI-I ≤ 2) as the outcome on which to compare CBT and Yoga at posttreatment and at follow-up. Since some attrition may occur, we will use last observation carried forward to insure an intent-to-treat analysis. The non-inferiority margin will be half the difference in response rates between the active comparison (CBT) and placebo. Based on earlier literature, we can expect response rates in our particular CBT and placebo conditions of 57.9% in CBT and 22.2% in placebo. Thus, our non-inferiority margin will be set at ¹/₂ the difference between 56.7 and 22.2, or 17.85%. Using the power analysis program PASS 12, we find that the number of subjects required to obtain .80 power for the non-inferiority test comparing CBT and Yoga is 95 participants in each of the 2 conditions. We verified this number in a 1000 simulation Monte Carlo study using these same parameters. This number is higher than the number proposed in the original grant. Thus, we will increase the N per cell in CBT and Yoga to 95 (22 additional patients per site) to have adequate power for this non-inferiority test. While the original study was budgeted based on a lower number of participants, with careful management of costs we believe we can manage this increase in participants within the full study budget if awarded as proposed.

For the superiority tests (CBT vs. SE and Yoga vs. SE) on the secondary outcomes (which are continuous), we used the MRM power analysis program PinT 2.12. We assumed 25% missing data, and used data from our recent CBT trials (e.g., Stern et al., 2012) to estimate the variances and covariances needed for PinT. PinT indicated greater than .80 power to detect an effect size as small as d=.27, between a small (d=.20) and medium (d=.50) effect size.

We predict that changes in mindfulness will mediate changes in outcome over time for patients in the Yoga condition, and changes in cognitions will mediate changes in CBT. Plus, changes in RSA and cortisol may also mediate changes in outcome across conditions. We further predict that treatment condition will moderate the effect of Time on the mediators ("a" paths).

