The three treatment conditions (Yoga, CBT, and SE) will be coded using 2 dummy variable contrasts, with SE as the "reference" treatment. The first dummy variable will contrast Yoga vs. SE, and the second will contrast CBT to SE. Time will be coded as weeks since baseline. To test of differences between treatments at post-treatment (week 12), time will be centered at week 12 (in other words, our Time variable in our analysis will be computed as "time minus 12"). In MRM or GLMM analyses in which this Time centered variable is used, the significance of the dummy variable contrasts (Yoga vs. SE and CBT vs. SE) provides the test of the differences between treatment conditions at post-treatment. A similar approach can be used to test differences between treatment conditions at follow-up.

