This growth curve model will be used to test differences between treatment conditions for our primary outcome (response to treatment) and for CGI-S, since these outcomes are measured frequently enough (7 times during treatment) to accurately model the growth curve. However, the other secondary outcomes are measured at most3 times during treatment (baseline, week 6, post-treatment), with secondary sleep measures administered only twice (baseline and posttreatment), thus disallowing accurate assessment of their growth curve. Thus, these outcomes will use an MRM employing an ANOVA type design (see for example, Liu, Rovine, & Molenaar, 2012). In this kind of model, time is treated as a categorical variable (using2 dummy variables [one for each assessment except the baseline assessment] to code the 3 assessments). The three treatment conditions (Yoga, CBT, and SE) will be coded using the 2 dummy variable contrasts (Yoga vs. SE and CBT vs. SE). Interactions will be formed between each treatment condition contrast and each assessment dummy variable. This coding freely estimates the means for the outcome at each assessment, without any constraint from a specific growth curve. This design is similar to a 3 x 3 repeated measures ANOVA with the exception that it includes all patients that complete at least one assessment, the outcome can be dichotomous, the covariance structure of the repeated measures can take almost any form, and this approach assumes data are missing at random (MAR) or not missing completely at random (MCAR). The significance of the interaction between a treatment condition contrast (e.g., Yoga vs. SE) and an assessment dummy variable (e.g., for the post-treatment assessment) will test whether the change from baseline to that assessment is significantly different between the treatment conditions. Using this coding scheme, all contrasts between treatment conditions at all assessments are provided by this one analysis. Thus, this approach has the added benefit of having all contrasts between the treatment conditions at each assessment being conducted on the same sample.

Demographics and comorbid diagnoses will be used as covariates in all analyses and considered as possible moderators of outcome at each assessment. An additional moderator that will be investigated is homework adherence.

Planned Secondary Analysis of Sensitivity of Growth Curve Model for Primary Outcome

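### The stated power above .80 at d=.27 against stress education cannot be reproduced for 95 vs 40: on the planned change contrast it needs a baseline-to-post correlation of about 0.87 to 0.90, and the inputs are not printed

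*Combined protocol and SAP*

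**What the plan says.** Section 9.2, repeated in 9.5, covers both superiority comparisons with SE on the continuous secondary outcomes: "PinT indicated greater than .80 power to detect an effect size as small as d=.27". On inputs it says "We assumed 25% missing data, and used data from our recent CBT trials", without printing any variance, covariance or correlation. It does not give the alpha, the sidedness, the occasions, the SD that defines d, or the numbers per arm entered for this calculation.

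The allocation is in section 3: "Using superiority tests, yoga (N = 95) will be compared to SE (N = 40", with 95 also in CBT.

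Section 9.6 treats time as categorical for the continuous secondary outcomes other than CGI-S. The treatment-by-assessment interaction "will test whether the change from baseline to that assessment is significantly different between the treatment conditions". CGI-S goes with the primary outcome into the growth-curve model "and for CGI-S, since these outcomes are measured frequently enough (7 times during treatment" to fit a curve. There time is centred at week 12, and "the significance of the dummy variable contrasts (Yoga vs. SE and CBT vs. SE) provides the test of the differences between treatment conditions" at that point.

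**The concern.** An effect of .27 SD is small, and the smaller arm has only 40 patients. A plain two-group comparison of that size falls far short of .80 power, so the claim has to rest on a large gain from repeated measurement. On a change-from-baseline contrast the gain comes almost wholly from the baseline-to-post correlation, and the plan does not say what correlation it used.

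This is the only sensitivity figure given for SIGH-A, the core secondary measure, and the other continuous outcomes against SE. If it is too favourable, a null contrast with SE could be taken as evidence against effects that the design was unlikely to detect.

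**Working it through.** **Inputs from the plan.** 95 vs 40 (section 3); d = .27, power .80, 25% missing (9.2); contrast = arm difference in change from baseline to post-treatment (9.6).

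**Assumed, not in the plan.** Two-sided 0.05, equal SDs at baseline and post, the correlation r, the missingness pattern, everyone has a baseline, no covariates. Normal approximation throughout.

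**Step 1. Try to reproduce the stated figure without help from baseline.**
- SE factor: √(1/95 + 1/40) = √0.03553 = 0.1885.
- Complete data: .27/0.1885 = 1.432; 1.432 − 1.960 = −0.528; power 0.30.
- 25% lost: 0.1885/√0.75 = 0.2176; .27/0.2176 = 1.241; power 0.24.
- Detectable d at .80 power: 2.802 × 0.1885 = 0.53 complete; 2.802 × 0.2176 = 0.61 with 25% lost.
- Even 95 vs 95 with complete data gives .27/√(2/95) = 1.861, power 0.46.

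The 0.30 and 0.24 also apply if d is in SD-of-change units, because r then drops out.

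**Step 2. The change contrast, d in outcome-SD units.** The variance is V × (1/95 + 1/40), where
- complete data: V = 2(1 − r);
- 25% missing at post: V = 2(1 − r) + (1 − R²)/3. Here R² is the squared multiple correlation of the post score with the visits still seen in those patients, and 1/3 = 1/0.75 − 1. If they have a baseline only, R² = r².

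For .80 power at .27, V must be at most (.27/0.528)² = 0.2614.
- Complete: r = 1 − 0.2614/2 = 0.869.
- 25% with baseline only: 2(1 − r) + (1 − r²)/3 = 0.2614, so r = 0.901.
- 25% missing post only, week 6 seen: r = 0.895 with equal correlations (R² = 2r²/(1 + r)); r = 0.888 with decaying correlations (R² = r).

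**Step 3. Power and detectable d over r (25% with baseline only).** Detectable d = 0.528√V; power = Φ(1.432/√V − 1.960).

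| r | V | detectable d | power at .27 |
|---|---|---|---|
| 0.5 | 1.250 | 0.59 | 0.25 |
| 0.6 | 1.013 | 0.53 | 0.30 |
| 0.7 | 0.770 | 0.46 | 0.37 |
| 0.8 | 0.520 | 0.38 | 0.51 |
| 0.9 | 0.263 | 0.27 | 0.80 |

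Simulation (4,000 runs) gave .24/.37/.52/.79 at r = .5/.7/.8/.9.

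**Step 4. What the plan's own data suggest.** The GAD pilot in section 2.2 (n = 16) prints t and d, with d scaled by the baseline SD. So SD(change)/SD(pre) = d/(t/4), and with equal SDs r = 1 − ratio²/2.
- Anxiety: .86/1.220 = .705, r = .75 (95% interval .41 to .91).
- Depression: .96/1.245 = .771, r = .70 (.32 to .89).
- Global severity: .76/1.145 = .664, r = .78 (.46 to .92).

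**Step 5. CGI-S, if the statement is meant to cover it.** Take the week-12 level from a linear curve over seven visits (weeks 0, 2, …, 12), equal correlation, complete data, no covariates. With uncorrelated visits, V = 1/7 + 36/112 = 0.464, and power at .27 is 0.56, the most this model can give. With correlation r, V = r + (1 − r) × 0.464. Power is .44/.39/.35/.31 at r = .3/.5/.7/.9, so here a higher correlation lowers power.

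**The case against.** The strongest reply is that nothing here shows an error. The plan names its software, its missing-data allowance and the source of its variances. With the covariances, alpha, sidedness and metric of d unseen, a correct run could have returned .27. That stands: the demonstrable fault is an unsupported figure. A reader might infer that .27 is simply wrong, and the documents do not support that.

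Other readings of the calculation help only in part. A one-sided 0.05 test lowers the required correlation to 0.834 (complete) or 0.858 to 0.874 (25% missing), but the plan nowhere states a one-sided superiority test. A linear slope over seven visits needs about 0.80 complete, or 0.82 to 0.85 with 25% missing. Section 9.6 does not assign that test to SIGH-A or the other categorical-time outcomes.

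A reader might also infer that the pilot contradicts the claim. It does not: its point estimates are lower, but with 16 patients the intervals reach the required region. Nor does the cohort level in section 9.6 by itself make matters worse, since a time-constant cohort intercept cancels from a change contrast. Only a cohort effect on change would cost power, and the plan gives no size for one.

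Whether the statement covers CGI-S is uncertain. It is absent from the secondary-outcome list in 9.5.2, and only the wording of 9.6 suggests that it belongs there.

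Finally, these are secondary outcomes, the figure sizes nothing, and a finished contrast is read from its confidence interval. That limits the consequence but is no reason to leave the figure as it is.

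**Conclusion.** The concern holds as one of an unsupported figure. For 95 vs 40 on the planned change contrast (two-sided 0.05, d in outcome-SD units, equal SDs), power of .80 at .27 requires a baseline-to-post correlation of about 0.87 with complete data and 0.89 to 0.90 with 25% missing. At 0.5 to 0.8 the design detects roughly 0.6 down to 0.4 SD. In SD-of-change units no correlation rescues the claim.

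The conclusion rests on the assumed alpha, equal SDs and missingness pattern, and the printed inputs could overturn it. It does not touch the primary response outcome, the 95-per-arm non-inferiority size or the planned analyses.

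**What to change.** - Re-run the calculation for 95 vs 40 on the section 9.6 post-treatment change contrast with 25% missing.
- Replace d=.27 in 9.2 and 9.5 with the resulting detectable d over a stated range of correlations. Keep .27 only if the inputs support it for 95 vs 40.
- Print with it the numbers per arm, occasions, covariance values and their source, alpha, sidedness and metric of d.
- If clustering is included, define the ICC as that of the change score, or specify a cohort-by-time effect.
- If the statement is meant to cover CGI-S, give it a separate figure for the week-12 contrast.

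The cost is one re-run and a few lines of protocol text. No patients are added and no analysis changes. The stated sensitivity against SE will probably become less favourable.

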9.3 Definition of Populations

Our primary analyses will use mixed-effects regression models (MRMs) with a logistic linking function (a GLMM analysis) since our primary outcome measure is dichotomous (treatment response). Analyses of secondary outcomes will be performed using MRM. MRM and GLMM easily accommodate nesting of repeated observations within subjects, include all who complete at least one assessment (including the baseline assessment), and are the preferred method to analyze longitudinal data (Hamer and Simpson, 2009 [135]). Our intent-to-treat sample includes all randomized patients who complete at least one assessment. Thus, our primary analyses (GLMM and MRM) are intent-to-treat analyses. We will also perform "per protocol" analyses. Our per protocol population will include all randomized patients who complete the baseline and post-treatment assessments, miss no more than 2 treatment sessions, who average a 4 or higher on the homework compliance scale, and who did not initiate prohibited treatment during the study. We will repeat our GLMM and MRM analyses using the per protocol sample.

9.4 Interim Analyses and Study Stopping Rules

No interim analyses are planned, unless requested by the DSMB or NCCAM. DSMB reports for safety will be prepared yearly (see DSMP) without unblinded treatment outcomes analyses unless specifically requested by the DSMB. Unexpected, serious, and intervention-related SAEs will be reported to the NYU, BU, and MGH IRBs, DSMB, and NCCAM, in accordance with requirements. In addition, all study treatment discontinuations for clinical worsening will be reported to the DSMB. If at any time during the course of the study, the DSMB judges that risk

to subjects outweighs the potential benefits, the DSMB shall have the discretion and responsibility to recommend that the study be terminated.

9.5 Outcomes

As noted earlier, a non-inferiority test is the most direct test of our hypothesis that Yoga will be as effective as CBT for both short-term and long-term outcomes. We will perform a non-inferiority test using response rate (response rate is defined as CGI-I \leq 2) as the outcome on which to compare CBT and Yoga at post-treatment and at follow-up. Since some attrition may occur, we will use last observation carried forward to insure an intent-to-treat analysis. The non-inferiority margin will be half the difference in response rates between the active comparison (CBT) and placebo. Based on earlier literature, we can expect response rates in our particular CBT and placebo conditions of 57.9% in CBT and 22.2% in placebo. Thus, our non-inferiority margin will be set at 1/2 the difference between 56.7 and 22.2, or 17.85%. Using the power analysis program PASS 12, we find that the number of subjects required to obtain .80 power for the non-inferiority test comparing CBT and Yoga is 95 participants in each of the 2 conditions. We verified this number in a 1000 simulation Monte Carlo study using these same parameters. This number is higher than the number proposed in the original grant. Thus, we will increase the N per cell in CBT and Yoga to 95 (22 additional patients per site) to have adequate power for this non-inferiority test. While the original study was budgeted based on a lower number of participants, with careful management of costs we believe we can manage this increase in participants within the full study budget if awarded as proposed.

For the superiority tests (CBT vs. SE and Yoga vs. SE) on the secondary outcomes (which are continuous), we used the MRM power analysis program PinT 2.12. We assumed 25% missing data, and used data from our recent CBT trials (e.g., Stern et al., 2012) to estimate the variances and covariances needed for PinT. PinT indicated greater than .80 power to detect an effect size as small as d=.27, between a small (d=.20) and medium (d=.50) effect size.

9.5.1 Primary Outcome

Response (CGI-I of 1 or 2) will serve as the primary outcome measure alongside the SIGH-A as the core secondary continuous measure.

9.5.2 Secondary Outcomes

Secondary Outcomes: Secondary outcome measures include the STAI, PSS, BDI-II and BAI, WHOQOL-BREF, PSQI, ISI, ASQ, and PSWQ. The FFMQ, MCQ, RSA, and cortisol are examined as possible mediators of change.

The Credibility/Expectancy Questionnaire will be administered to examine whether credibility and expectancy moderates therapy outcome.

In addition, we will explore whether clinical characteristics (comorbid diagnoses) and demographic characteristics (age, sex, SES) are possible moderators. The data analyses are described for the primary measure only.

9.6 Data Analyses

Primary Analyses

Our primary analyses will use mixed-effects regression models (MRMs) with a logistic linking function (a GLMM analysis) since our primary outcome measure (response to treatment, defined as CGI-I≤2) is dichotomous. Analyses of secondary outcomes will be performed using MRM. MRM and GLMM easily accommodate nesting of repeated observations within subjects, include all subjects with at least one assessment, and are the preferred method to analyze longitudinal data (Hamer and Simpson, 2009 [135]). Since these analyses will include all subjects who are randomized and complete at least one assessment, it is an intent-to-treat analysis. Also, since subjects will undergo treatment in groups (4-6 subjects per group) our MRM and GLMM models will include 3 levels: repeated measurements (level 1) nested within subjects (level 2) who will be nested within their treatment cohort (level 3).

Our primary model will be a GLMM in which response to treatment over time will be modeled as a growth curve. Our primary analyses will examine outcomes at post-treatment (Aim 1). These analyses will include only the 7 assessments from baseline to post-treatment, and will not include the follow-up (FU) assessment since it could be affected by subjects seeking other treatments during the FU period. Only our exploratory analyses for outcome at FU (Aim 2) will include data from the FU assessment. Since recent research indicates that suboptimal modeling of the growth curve can result in incorrect results, we will examine various linear and nonlinear models to find the optimal growth curve during treatment (linear, quadratic, cubic, exponential [leveling off at an asymptote], and an ANOVA model, in which time is coded as a categorical variable. For this ANOVA model, each assessment time point is modeled with a dummy coded assessment variable [coded 1 for the assessment, 0 for other assessments]. In this model, the means at each assessment point are freely estimated and are not constrained to fit any particular pattern. See our discussion of the ANOVA model in the paragraph below for more information).We will conduct our significance tests using the growth curve that most accurately models the data (comparing the various growth curve models using AIC and BIC).

The three treatment conditions (Yoga, CBT, and SE) will be coded using 2 dummy variable contrasts, with SE as the "reference" treatment. The first dummy variable will contrast Yoga vs. SE, and the second will contrast CBT to SE. Time will be coded as weeks since baseline. To test of differences between treatments at post-treatment (week 12), time will be centered at week 12 (in other words, our Time variable in our analysis will be computed as "time minus 12"). In MRM or GLMM analyses in which this Time centered variable is used, the significance of the dummy variable contrasts (Yoga vs. SE and CBT vs. SE) provides the test of the differences between treatment conditions at post-treatment. A similar approach can be used to test differences between treatment conditions at follow-up.

This growth curve model will be used to test differences between treatment conditions for our primary outcome (response to treatment) and for CGI-S, since these outcomes are measured frequently enough (7 times during treatment) to accurately model the growth curve. However, the other secondary outcomes are measured at most3 times during treatment (baseline, week 6, post-treatment), with secondary sleep measures administered only twice (baseline and posttreatment), thus disallowing accurate assessment of their growth curve. Thus, these outcomes will use an MRM employing an ANOVA type design (see for example, Liu, Rovine, & Molenaar, 2012). In this kind of model, time is treated as a categorical variable (using2 dummy variables [one for each assessment except the baseline assessment] to code the 3 assessments). The three treatment conditions (Yoga, CBT, and SE) will be coded using the 2 dummy variable contrasts (Yoga vs. SE and CBT vs. SE). Interactions will be formed between each treatment condition contrast and each assessment dummy variable. This coding freely estimates the means for the outcome at each assessment, without any constraint from a specific growth curve. This design is similar to a 3 x 3 repeated measures ANOVA with the exception that it includes all patients that complete at least one assessment, the outcome can be dichotomous, the covariance structure of the repeated measures can take almost any form, and this approach assumes data are missing at random (MAR) or not missing completely at random (MCAR). The significance of the interaction between a treatment condition contrast (e.g., Yoga vs. SE) and an assessment dummy variable (e.g., for the post-treatment assessment) will test whether the change from baseline to that assessment is significantly different between the treatment conditions. Using this coding scheme, all contrasts between treatment conditions at all assessments are provided by this one analysis. Thus, this approach has the added benefit of having all contrasts between the treatment conditions at each assessment being conducted on the same sample.

Demographics and comorbid diagnoses will be used as covariates in all analyses and considered as possible moderators of outcome at each assessment. An additional moderator that will be investigated is homework adherence.

Planned Secondary Analysis of Sensitivity of Growth Curve Model for Primary Outcome

To determine if the results of the analyses for Aim 1 are sensitive to the growth curve model, we will perform a secondary analysis, using a simple ANCOVA-type model, to verify the results of our primary growth curve model. Since the outcome is binary (response to treatment), this analysis will be performed using logistic regression, with the following predictors of outcome at post-treatment: baseline severity based on the CGI-S and SIGH-A, and the two dummy variables coding the contrast between SE and the 2 active treatments. This analysis will be performed twice: once as an ITT analysis with missing outcomes imputed as last observation carried forward, and once as a completer analysis.

Per Protocol Secondary Analysis:

As additional secondary analyses, we will repeat our GLMM and MRM analyses using the per protocol sample. We will use these analyses rather than simpler analyses (such as logistic regression or repeated measures ANOVA) because repeating our GLMM and MRMs will allow a more direct comparison to the results for the intent-to-treat sample, allows inclusion of subjects that miss some assessments (other than baseline and post-treatment), allows the modeling of complex covariances between the repeated measures, and it assumes MAR rather than MCAR.

Follow Up Secondary Analyses:

Analyses of outcome at FU (Aim 2) will be considered exploratory since subjects may seek additional treatment during follow-up. These analyses will follow the analyses of outcome at post-treatment, except one additional assessment (FU) will be added to these analyses. Since response during FU may not follow the growth curve of the treatment phase, the growth curve for Aim 2 will be modeled as "piecewise", separately modeling the growth curve during treatment and follow-up. (Analyses of the secondary outcomes at FU will follow the mixed effects ANOVA model described above since these analyses include only 4 total assessments). We will add an additional dummy variable predictor to the analyses for Aim 2, coding whether or not the subject received additional treatment during FU. We will also add the interactions of this "additional treatment" variable with all the other predictors in the analyses to determine if "additional treatment" impacted response to treatment at FU. This analysis will

allow us to assess the effect of CBT vs. SE and Yoga vs. SE separately for those who received additional treatment and those who did not. A further analysis will compare the rates at which subjects in the 3 conditions seek additional treatment during the FU period.

Secondary Mediation Analysis for Primary Outcome:

We are interested in mediation of our primary outcome: response at post-treatment. Thus, this analysis will include all assessments through and including post-treatment (but not FU). Our mediation analysis includes 2 independent variables (the contrast of Yoga vs. SE and the contrast of CBT vs. SE) and 3 mediators: mindfulness, vagal tone, and maladaptive cognitions. The "a" paths in the mediation analysis will be the effects of each of the 2 independent variables on each of the 3 mediators. These paths will be derived from three MRMs, one for each mediator as the dependent variable. These MRMs will be identical to the models described above with Time centered at post-treatment. Thus, the effect of each contrast (Yoga vs. SE and CBT vs. SE) will be their effect on each mediator at post-treatment. The "b" paths will be derived from the GLMM model (described above) for differences between treatment conditions at post-treatment, with the dependent variable being "response". The 3 mediators will be included in this growth curve model as additional simultaneous predictors of response. The regression coefficients for the mediators in this analysis become the "b" paths in the mediation analysis (the paths from each mediator to outcome). Significance of mediated pathways will be determined using biascorrected bootstrap mediation analysis (e.g., Fritz and MacKinnon, 2007 [137]). We predict that changes in mindfulness will mediate changes in outcome over time for patients in the Yoga condition, and changes in cognitions will mediate changes in CBT. Plus, changes in RSA and cortisol may also mediate changes in outcome across conditions.

Missing Data. Although we will make every effort to reduce missingness, it is inevitable that some data will be missing. We will use pattern mixture modeling (Hedeker & Gibbons, 2006; Enders, 2011 [138-139]) and rerun our analyses coding for various missing data patterns (no missing data, early dropouts, late dropouts, FU dropouts, etc.) to determine both if missingness impacts our findings and how the differences between treatment conditions depend on the missing data pattern.

